9.2.3 Preparation and Administration

9.2.3.1 For Intravenous Administration

Relatlimab Injections

Relatlimab injections (10 mg/mL) are to be administered as an IV infusion through a compatible low-protein binding in-line filter at the protocol-specified doses. They are not

to be administered as an IV push or bolus injection. Relatlimab injection can be diluted with 0.9% (w/v) sodium chloride injection (normal saline, NS) or 5% (w/v) dextrose injection (D5W) to protein concentrations no lower than 0.2 mg/mL.

Care must be taken to assure sterility of the prepared solution, as the product does not contain any anti-microbial preservative or bacteriostatic agent. No incompatibilities have been observed between relatlimab injection and ethylvinyl acetate (EVA), polyolefin (PO) or polyvinyl chloride (PVC) IV containers, di(2-ethylhexyl)phthalate (DEHP)-plasticized PVC IV sets, DEHP-free IV sets, or in-line filters with 0.2 µm or 1.2 µm polyethersulfone (PES), 0.2 µm nylon, or 0.2 µm polyvinylidene fluoride (PVDF) membranes.

Detailed instructions for drug product dilution and administration are provided in the pharmacy manual for the clinical study.

Co-administration of Relatlimab Injection and Nivolumab Injection

Relatlimab injections (10 mg/mL) can be co-administered with nivolumab injection (also referred to as BMS-936558 injection) as an IV infusion through a compatible low-protein-binding in-line filter at the protocol-specified doses. Relatlimab injection combined with nivolumab injection can be diluted with NS or D5W to a total protein concentration no lower than 0.8 mg/mL (0.2 mg/mL of relatlimab and 0.6 mg/mL of nivolumab).

Care must be taken to assure sterility of the prepared solution, as the products do not contain any anti-microbial preservative or bacteriostatic agent. No incompatibilities between the combined drug products and EVA, PO, or PVC IV containers, DEHP-plasticized PVC IV sets, DEHP-free IV sets and in-line filters with 0.2 µm or 1.2 µm PES, 0.2 µm nylon, or 0.2 µm PVDF membranes.

Detailed instructions for drug product dilution and administration are provided in the pharmacy manual for the clinical study.

9.2.4 Packaging, Labeling, and Storage

Upon supply to site, study drugs will be labeled “for investigational use only” as per FDA regulations.

9.2.4.1 For Intravenous Administration

Relatlimab Injection, 10 mg/mL

The drug products should be stored at 2°C to 8°C (36°F to 46°F) with protection from light. Do not freeze the drug products.

Relatlimab Injection Infusions and Combinations of Relatlimab Injection and Nivolumab Injection Infusions

The IV administration of relatlimab infusions or combined relatlimab and nivolumab infusions must be completed within 24 hours of preparation. If not used immediately, the infusion solutions may be stored in a refrigerator at 2°C to 8°C (36°F to 46°F) for up to 24 hours and a maximum of 4 hours of the total 24 hours can be at room temperature

(15°C to 25°C; 59°F to 77°F) and exposed to room light. The maximum 4-hour period under room temperature and room light conditions includes the product administration period.

9.3 Disposal and Destruction

All unused and/or partially used Investigational Medicinal Product will be destroyed on site as per Institutional SOP and the destruction documented. Copy of the drug destruction document will be provided to BMS. IMP handling document will be provided at the time of Study activation.

10 SCHEDULE OF ASSESSMENTS

10.1 Screening

Screening assessments are to be conducted within 28 days prior to initiating study unless otherwise specified. At screening, the following procedures/tests will be performed:

- Informed Consent
- Eligibility (Inclusion/Exclusion criteria)
- Demographic and medical history
- Prior and concomitant medication review
- Physical Exam
- Vital Signs: systolic and diastolic blood pressures, and temperature
- ECOG Performance Status
- 12-Lead ECG
- Echocardiogram
- Laboratory Evaluations
 - Pregnancy Test (Urine or Serum β -HCG²)
 - CBC with differential
 - Comprehensive metabolic panel
 - LDH
 - T3, free T4, TSH
 - ACTH and serum cortisol
 - Amylase
 - Lipase
 - Urinalysis
 - HBsAg, HBsAb, Hep C Ab, HB core antibody
 - Troponin T
 - PT/INR
 - PTT
- CT chest plain
- MRI brain with and without contrast
- MRI abdomen and pelvis with and without contrast (EOVIST® preferred)
- Correlative studies
 - Blood
 - Archival tissue
 - Fresh tumor biopsy if needed, safe and feasible as determined by investigator

10.2 Cycle 1, 3, 5, 7, Day 1 + or – 3 days

The following assessments will be performed

- Review adverse events
- Review concomitant medication

- Physical Exam
- Vital Signs: systolic and diastolic blood pressures, and temperature
- ECOG Performance Status
- Administration of nivolumab plus relatlimab
- Laboratory Evaluations
 - Pregnancy Test (Urine or Serum β -HCG²)
 - CBC with differential
 - Comprehensive metabolic panel
 - LDH
 - Amylase
 - Lipase
 - Urinalysis
 - Troponin T (Only cycle 1)
- CT chest plain (Only for cycles 3,5,7, Day 1 (+ or – 3 days))
- MRI abdomen and pelvis with and without contrast (EOVIST® preferred) (Only for cycles 3,5,7, Day 1 (+ or – 3 days))
- Correlative studies
 - Blood for correlative studies to be obtained on
 - Cycle 1, Day 1 (+ or – 3 days)
 - Cycle 3, Day 1 (+ or – 3 days)
 - upon progression or response
 - Fresh tumor biopsy if needed, safe and feasible as determined by investigator.

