5.2 Dosing and Administration

Enrolled patients will be treated in the outpatient setting. Nivolumab 480 mg will be mixed in the same bag with Relatlimab 160 mg and will be administered intravenously over 60 minutes (+ or –5 minutes) every 4 weeks. Each cycle will be approximately 4 weeks in length. Both drugs will be administered until disease progression or intolerable toxicity for up to 24 months.

Table 2. **Dosing and Administration Schedule Nivolumab + Relatlimab Combination Treatment (All cycles)**

Drug	Dose	Day 1 (+/- 3 days)	Day 28 (+/- 3 days)
Nivolumab	480 mg	X	X
Relatlimab	160 mg	X	X

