5.3 Missed doses

Patients who miss a nivolumab plus relatlimab dose at the usual required time should skip additional therapy until the next cycle.

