7 TREATMENT DISCONTINUATION AND ADVERSE EVENT MANAGEMENT

Dose reductions or dose escalations are not permitted in this study. Dose delay criteria as noted below apply for all drug-related adverse events regardless of whether or not the event is attributed to nivolumab, relatlimab, or both. All study drugs must be delayed until treatment can resume. Reasons for permanent treatment discontinuation include the following:

- Any drug-related/immune-related Grade 4 toxicity, except for endocrinopathy and asymptomatic elevations of amylase and lipase.
- Any Grade 3 elevation of liver function tests or colitis not responding to steroids, infliximab and/or mycophenolate mofetil.
- Any other drug-related/immune-related Grade 3 toxicity, **EXCLUDING:**
 - *Grade 3 nausea/vomiting controlled by medical intervention within 72 hours*
 - *Grade 3 immune-related AEs (other than ocular events, colitis, myocarditis and pneumonitis) that improve to Grade \leq 1 or baseline within 14 days after the initiation of supportive care or corticosteroid therapy*
 - *Grade 3 endocrinopathy that is managed with or without systemic corticosteroid therapy and/or hormone replacement therapy and the subject is asymptomatic or minimally or transiently symptomatic based on Investigator assessment*
 - *Grade 3 fatigue lasting \leq 7 days from onset*
 - *Grade 3 rash in the absence of desquamation, with no mucosal involvement, that does not require systemic steroids, that does not interfere with activities of daily living and resolves to Grade 1 by the next dose of scheduled treatment or 14 days, whichever is longer*
 - *Any grade vitiligo or alopecia*
- Grade 2 or higher episcleritis, uveitis, or iritis
- Grade 2 pneumonitis that does not resolve to \leq Grade 1 within 3 days of initiation of maximal supportive treatment.

If treatment is withheld > 6 weeks from the last dose, the participant must be permanently discontinued from study therapy.

Table 3. Adverse Event Management Rules

Toxicity	Hold Treatment For Grade	Timing for Restarting Treatment	Treatment Discontinuation
Diarrhea/Colitis	2-3	Toxicity resolves to Grade 0-1	Toxicity does not resolve within 6 weeks of last dose or inability to reduce corticosteroid to 10 mg or less of prednisone or equivalent per day within 12 weeks
	4	Permanently discontinue	Permanently discontinue
AST, ALT, or Increased Bilirubin	2	Toxicity resolves to Grade 0-1	Toxicity does not resolve within 6 weeks of last dose

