10.4 Subsequent Treatment Cycles

Subsequent treatment cycles are to be repeated every 4 weeks until progression or toxicity up to 24 months. Cycles will follow the schedule of assessments outlined in section 10.2 (odd cycles) and section 10.3 (even cycles)

10.5 End of Treatment Visit, 28 days after the last dose of Nivolumab and Relatlimab combination treatment (+ or – 14 days)

The following assessments will be performed during the end of treatment visit:

- Review adverse events
- Review concomitant medication
- Physical Exam
- Vital Signs: systolic and diastolic blood pressures, and temperature
- ECOG Performance Status
- Laboratory Evaluations
 - Pregnancy Test (Urine or Serum β -HCG²)
 - CBC with differential
 - Comprehensive metabolic panel
 - LDH
 - T3, free T4, TSH
 - ACTH and serum cortisol
 - Amylase
 - Lipase
 - Urinalysis

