12.7 Progression-Free Survival

Defined as the period from the date of study entry until disease progression or death (whichever occurs first). Cases who have not had an event will be censored at the date of last disease assessment documenting the patient was free of progression. Progression will be evaluated by RECIST v1.1.

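### Body scans are tied to dosing cycles with no calendar anchor, so toxicity holds can move them and make PFS and duration-of-response timing depend on toxicity

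*Combined protocol and SAP*

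**What the plan says.** Section 10.2 places chest CT and abdomen/pelvis MRI by cycle number, "Only for cycles 3,5,7, Day 1", within 3 days either side. The study calendar in Section 10.8 agrees. Section 10.4 extends the pattern: "Cycles will follow the schedule of assessments outlined in section 10.2 (odd cycles) and section 10.3 (even cycles"). Body imaging therefore falls on Day 1 of every odd cycle from cycle 3. Section 5.2 gives the cycle length: "Each cycle will be approximately 4 weeks in length".

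For toxicity, Section 7 says "All study drugs must be delayed until treatment can resume", with an outer limit: "If treatment is withheld > 6 weeks from the last dose, the participant must be permanently discontinued from study therapy". For a missed dose, Section 5.3 says the patient "should skip additional therapy until the next cycle". Section 6.3 adds a separate ground for withdrawal: being unable to receive the combination for 2 cycles over 12 weeks. None of these sections says whether scans keep their date.

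The only tumour imaging with a calendar interval is the brain MRI, every 6 months (Section 10.8, footnote 6).

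On endpoints, Section 16.3 ends PFS at documented objective progression or death and starts duration of response at the first documented response. Section 12.7 adds the censoring rule: "Cases who have not had an event will be censored at the date of last disease assessment documenting the patient was free of progression". PFS is estimated by Kaplan-Meier at pre-specified times, which are not named. No sensitivity analysis for shifted assessments is described.

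**The concern.** PFS, duration of response and the censoring date are all read from scan dates. If a scan moves whenever a dose is held, the assessment schedule differs between patients with and without toxicity, and does so for a reason that may itself be related to response. In a single-arm trial this cannot bias a comparison between arms. It does affect how PFS compares with the historical medians of 2.6 to 3.3 months quoted in Section 1.1. Those medians are short relative to an 8-week scan interval, so the placing of one scan matters.

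**Working it through.** **The plan's own figure.** The documents give no PFS figure to reproduce. They do state the Simon design in Section 1.6: stop if there are 0 responses in 13, reject the null at 4 or more in 27, type I error 0.0416, power 0.8011. The probability of rejection is the sum over x = 1 to 13 of P(X₁ = x) × P(X₂ ≥ max(0, 4 − x)), with X₁ ~ Bin(13, p) and X₂ ~ Bin(14, p). This gives 0.0416 at p = 0.05 and 0.8011 at p = 0.20, matching the protocol. Scan dates do not enter the formula.

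**Scan dates.** Inputs: 4-week cycles (Section 5.2), a 6-week limit from the last dose (Section 7), body scans at odd cycles from cycle 3 (Sections 10.2 and 10.4). One hold adds at most 6 − 4 = 2 weeks.

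| Holds before cycle 3 | Cycle 3 scan | Cycle 5 scan |
|---|---|---|
| None | week 8 | week 16 |
| One maximum hold | week 10 | week 18 |
| Two maximum holds | week 12 | week 20 |

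The window of 3 days is well short of 14 days.

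**Patients with holds.** Assumptions: exponential time to true progression, detection at the next scan, scans exactly on the day, time counted from Cycle 1 Day 1. With 52.1775/12 = 4.348 weeks per month, a true median of 2.6 months is 11.3 weeks and S(t) = 0.5^(t/11.3). The observed PFS at a given week equals S at the last scan on or before it. The apparent median is the first scan by which at least half have progressed.

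- No hold: 1 − S(8) = 0.39 and 1 − S(16) = 0.63, so the apparent median is week 16 (3.68 months). Week-16 PFS reads S(16) = 0.37.
- One hold: 1 − S(10) = 0.46, so the median moves to week 18 (4.14 months). Week-16 PFS reads S(10) = 0.54. Week-26 PFS reads S(26) = 0.20 against S(24) = 0.23 on schedule, which is lower.
- Two holds: 1 − S(12) = 0.52, so the median falls to week 12 (2.76 months). At a true median of 2.8 months, 1 − S(12) = 0.495, and the median instead rises to week 20 (4.60 months).

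Mean detection is nonetheless later in every case. Simulation over true medians of 2.6, 2.8 and 3.3 months gives 0.45 to 0.56 weeks later with one early hold and 1.04 to 1.27 weeks later with two.

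**Whole cohort.** The documents give no hold rate, so 2-week holds were simulated at 5% to 30% per dose for the same three true medians.

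- The mean delay in detection is 0.14 to 0.79 weeks.
- The apparent median shifts by 0 to 0.46 months.
- Week-26 PFS changes by about −0.4 to +4 points.
- Week-16 PFS rises by 3 to 14 points if scans fall exactly on the day. Week 16 is itself a scan date, so this landmark is unusually sensitive. With scan days spread uniformly over the ±3-day window under both schedules and a true median of 2.6 months, about half the week-16 scans fall after week 16. The calendar schedule then reads about ½ × (0.612 + 0.375) = 0.49 (0.50 simulated), against 0.51 to 0.54 with cycle-tied scans: a difference of 1 to 5 points.

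For scale, the 95% half-width at 27 patients and a proportion of 0.375 is 1.96 × √(0.375 × 0.625/27) = 0.18.

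**The case against.** The strongest reply is that the shift is not established. Section 5.3 can be read as keeping cycles in their calendar place, so that a missed dose is skipped and Cycle 3 Day 1 stays at week 8. Section 7 speaks of delay instead, and the 12-week ground in Section 6.3 does not match the 6-week limit. The reply stands to this extent: the text supports a shift under the delay rule but does not settle how cycles are counted. That is itself part of the defect, because site staff cannot tell when a scan is due after a hold.

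It is also fair that two maximum holds before cycle 3 will be uncommon, since Section 7 and Table 3 send many toxicities straight to permanent discontinuation. PFS is secondary and descriptive, and its sampling error at 27 patients exceeds the cohort effect.

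Four stronger readings are tempting, and the documents do not support them:

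- A reader might infer that cycle-tied scans make PFS longer. Mean detection is later, but the two-hold case at a true median of 2.6 months shortens the apparent median from 16 to 12 weeks.
- A reader might divide a 2- to 4-week slip by the historical median PFS and call the result a bias. That sets one patient's delay against a cohort median and estimates no bias.
- A reader might infer that body imaging stops after cycle 7. Section 10.4 continues it in odd cycles.
- A reader might object that the window allows a dose before the scan that would show progression. Section 12.3 expressly provides for conditional treatment after progression on imaging, so this does not contradict the plan.

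**Conclusion.** The point holds as an inexpensive improvement to the secondary endpoints. Body imaging is anchored to dosing cycles, dosing may be delayed, and no section keeps the scans on calendar time. Under the delay rule the first scan can move by 2 weeks, or by 4 with two maximum holds. PFS and duration-of-response timing then depends on toxicity.

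Across the cohort the effect is modest: a mean delay of about 0.1 to 0.8 weeks, with no fixed direction for the apparent median. These sizes rest on exponential progression, 2-week holds and assumed hold rates of 5% to 30% per dose, without separate modelling of deaths. If the 12-week wording in Section 6.3 allowed a gap of that length, one gap could move a scan by 12 − 4 = 8 weeks; the text does not settle this.

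A reader might also infer that the primary analysis is compromised. It is not: best response rate, the Simon rule, the type I error of 0.0416 and the power of 0.8011 do not depend on scan dates when the scans are done.

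**What to change.** In Sections 10.2 and 10.4 and in the study calendar, state that on-treatment tumour imaging is done every 8 weeks counted from Cycle 1 Day 1, within the existing ±3-day window, regardless of dose delays or missed doses.

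Reconcile Section 5.3 (skip to the next cycle), Section 6.3 (2 cycles over 12 weeks) and Section 7 (delay, with a 6-week limit) so that they agree on how cycles are counted after a missed dose. Which rule should govern treatment is for the sponsor to decide.

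The cost is protocol wording. Patients dosed on time need no additional on-treatment scans. Patients with holds may need an occasional additional scan, or one that does not coincide with a dosing visit. Imaging after treatment stops is a separate question with its own cost and is not part of this change.

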10.3 Cycles 2, 4, 6, 8, Day 1 + or – 3 days

The following assessments will be performed at each cycle unless otherwise specified:

- Review adverse events
- Review concomitant medication
- Physical Exam
- Vital Signs: systolic and diastolic blood pressures, and temperature
- ECOG Performance Status
- Administration of nivolumab plus relatlimab
- Laboratory Evaluations
 - Pregnancy Test (Urine or Serum β -HCG²)
 - CBC with differential
 - Comprehensive metabolic panel
 - LDH
 - T3, free T4, TSH
 - ACTH and serum cortisol
 - Amylase
 - Lipase
 - Urinalysis

- Troponin T (Only cycle 2)
- Correlative Studies
 - Blood for correlative studies to be obtained on Cycle 2, Day 1 (+ or – 3 days)) upon progression or response
- Fresh tumor biopsy if needed, safe and feasible as determined by investigator..

10.4 Subsequent Treatment Cycles

Subsequent treatment cycles are to be repeated every 4 weeks until progression or toxicity up to 24 months. Cycles will follow the schedule of assessments outlined in section 10.2 (odd cycles) and section 10.3 (even cycles)

10.5 End of Treatment Visit, 28 days after the last dose of Nivolumab and Relatlimab combination treatment (+ or – 14 days)

The following assessments will be performed during the end of treatment visit:

- Review adverse events
- Review concomitant medication
- Physical Exam
- Vital Signs: systolic and diastolic blood pressures, and temperature
- ECOG Performance Status
- Laboratory Evaluations
 - Pregnancy Test (Urine or Serum β -HCG²)
 - CBC with differential
 - Comprehensive metabolic panel
 - LDH
 - T3, free T4, TSH
 - ACTH and serum cortisol
 - Amylase
 - Lipase
 - Urinalysis

10.6 Safety Follow-Up, 30 days (+ or – 7 days) post discontinuation

The following assessments will be performed during the end of treatment visit:

- Post-study anticancer therapy status
- Review adverse events
- Review concomitant medication
- Physical Exam
- Vital Signs: systolic and diastolic blood pressures, and temperature
- ECOG Performance Status
- Laboratory Evaluations
 - Pregnancy Test (Urine or Serum β -HCG²)

- CBC with differential
- Comprehensive metabolic panel
- LDH
- T3, free T4, TSH
- ACTH and serum cortisol
- Amylase
- Lipase
- Urinalysis

10.7 Survival Follow-Up, Every 12 weeks (+ or – 7 days) for 2 years

The following assessments will be performed during the survival follow-up visit:

- Post-study anticancer therapy status
- Survival status

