10.8 STUDY CALENDAR

Trial Period:	Screening Phase	Treatment Cycles								End of Treatment	Post-Treatment	
Treatment Cycle/Title:	Screening	1	2	3	4	To be repeated every 4 weeks until progression or toxicity up to 24 months				EOT (at time of discontinuation)	Safety Follow-up	Survival Follow-Up ¹
Scheduling Window (Days):	(-28 to -1 days)		± 3	± 3	± 3	± 3	± 3	± 3	± 3	± 3	30 days (+ or – 7 days) post discontinuation	Every 12 weeks (+ or – 7 days)
Administrative Procedures												
Informed Consent	X											
Inclusion/Exclusion Criteria	X											
Demographics and Medical History	X											
Prior and Concomitant Medication Review	X											
Post-study anticancer therapy status											X	X
Survival Status												X
Clinical Procedures/Assessments												
Review Adverse Events		X	X	X	X	X	X	X	X	X	X	
Review Concomitant Medication		X	X	X	X	X	X	X	X	X	X	
Physical Examination	X	X	X	X	X	X	X	X	X	X	X	
Vital Signs (temperature/pulse/respiratory rate/blood pressure and weight)	X	X	X	X	X	X	X	X	X	X	X	
ECOG Performance Status	X	X	X	X	X	X	X	X	X	X	X	
12-Lead ECG	X											
Echocardiogram	X											
Administration of nivolumab plus relatlimab over 60 minutes IV		X	X	X	X	X	X	X	X	X		
Laboratory Procedures/Assessments: analysis performed by LOCAL laboratory												
Pregnancy Test – Urine or Serum β-HCG ²	X	X	X	X	X	X	X	X	X	X	X	
CBC with Differential	X	X	X	X	X	X	X	X	X	X	X	

Trial Period:	Screening Phase	Treatment Cycles								End of Treatment	Post-Treatment		
		1	2	3	4	To be repeated every 4 weeks until progression or toxicity up to 24 months					EOT (at time of discontinuation)	Safety Follow-up	Survival Follow-Up ¹
Treatment Cycle/Title:	Screening					5	6	7	8				
Scheduling Window (Days):	(-28 to -1 days)		± 3	± 3	± 3	± 3	± 3	± 3	± 3	± 3	± 3	30 days (+ or - 7 days) post discontinuation	Every 12 weeks (+ or - 7 days)
Comprehensive Serum Chemistry Panel	X	X	X	X	X	X	X	X	X	X	X	X	
LDH	X	X	X	X	X	X	X	X	X	X	X	X	
T3, freeT4 and TSH ³	X		X		X		X		X		X	X	
ACTH and serum cortisol ³	X		X		X		X		X		X	X	
Amylase ³	X	X	X	X	X	X	X	X	X	X	X	X	
Lipase ³	X	X	X	X	X	X	X	X	X	X	X	X	
Urinalysis	X	X	X	X	X	X	X	X	X	X	X	X	
HBsAg, HBsAb, Hep C Ab, HB core antibody ⁴	X												
Troponin T ^{3,5}	X	X	X										
PT/INR and PTT	X												
Efficacy Measurements													
CT chest plain	X			X		X		X					
MRI Brain with and without contrast ⁶	X												
MRI abdomen/ pelvis with EOVIST™ with and without contrast ⁷	X			X		X		X					

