13.3 Non-Serious Adverse Event

- Non-serious Adverse Events (AE) are to be provided to BMS in aggregate via interim or final study reports as specified in the agreement or, if a regulatory requirement [e.g., IND US trial] as part of an annual reporting requirement.
- Non-serious AE information should also be collected from following the subject's written consent to participate in the study.

Non-serious Adverse Event Collection and Reporting

The collection of non-serious AE information should begin following the subject's written consent to participate in the study. All non-serious adverse events (not only those deemed to be treatment-related) should be collected continuously during the treatment period and for a minimum of (100 days) days following the last dose of study treatment.

Non-serious AEs should be followed to resolution or stabilization, or reported as SAEs if they become serious. Follow-up is also required for non-serious AEs that cause interruption or discontinuation of study drug and for those present at the end of study treatment as appropriate.

Laboratory Test Abnormalities

All laboratory test results captured as part of the study should be recorded following institutional procedures. Test results that constitute SAEs should be documented and reported to BMS as such.

The following laboratory abnormalities should be documented and reported appropriately:

- any laboratory test result that is clinically significant or meets the definition of an SAE
- any laboratory abnormality that required the participant to have study drug discontinued or interrupted
- any laboratory abnormality that required the subject to receive specific corrective therapy.

It is expected that wherever possible, the clinical rather than laboratory term would be used by the reporting investigator (eg, anemia versus low hemoglobin value).

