13.4.4 Time Period and Frequency for Event Assessment and Follow-Up

The occurrence of an adverse event (AE) or serious adverse event (SAE) may come to the attention of study personnel during study visits and interviews of a study participant presenting for medical care, or upon review by a study monitor.

All AEs will be captured on the appropriate case report form (CRF) as well as in the Adverse Event reporting section in Velos, a HIPAA AND 21 CFR part 11 compliant database and will be reported to the University of Miami's IRB per institutional requirements.

Any medical condition that is present at the time that the participant is screened will be considered as baseline and not reported as an AE. However, if the study participant's condition deteriorates at any time during the study, it will be recorded as an AE.

Changes in the severity of an AE will be documented to allow an assessment of the duration of the event at each level of severity to be performed. AEs characterized as intermittent require documentation of onset and duration of each episode.

Study personnel will record all reportable events with start dates occurring any time after informed consent is obtained until 7 (for non-serious AEs) or 30 days (for SAEs) after the last day of study participation. At each study visit, the investigator will inquire about the occurrence of AE/SAEs since the last visit. Events will be followed for outcome information until resolution or stabilization.

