13.6 Serious Adverse Event Reporting

Generally, any AE considered serious by the PI or Sub-investigator or which meets the definition of an SAE included in **Section 13.2, Definition of Serious Adverse Events**.

SAEs will be captured on the appropriate case report form (CRF) as well as in the Serious Adverse Event reporting section in Velos, a HIPAA AND 21 CFR part 11 compliant database and will be reported to the University of Miami's IRB per institutional requirements.

All SAEs that occur following the subject's written consent through 100 days of discontinuation of dosing must be reported to BMS Worldwide Safety, whether related or not related to study drug. SAEs will be reported to BMS Worldwide safety using the Medwatch 3500A Reporting form. The Sponsor-Investigator or designee will report the SAE to BMS Worldwide **within 24 hours of his/her becoming aware of these events regardless of relationship of the SAE to the use of study drug.**

According to 21 CFR 312.32(c)(1), "the sponsor must notify FDA in an IND safety report of potential serious risks, from clinical trials or any other source, as soon as possible, but in no case later than 15 calendar days after the sponsor determines that the information qualifies for reporting... In each IND safety report, the sponsor must identify all IND safety reports previously submitted to FDA concerning a similar suspected adverse reaction and must analyze the significance of the suspected adverse reaction in light of previous, similar reports or any other relevant information. The sponsor must report any suspected adverse reaction that is both serious and unexpected. The sponsor must report an adverse event as a suspected adverse reaction only if there is evidence to suggest a causal relationship between the drug and the adverse event, such as:

- (A) A single occurrence of an event that is uncommon and known to be strongly associated with drug exposure (e.g., angioedema, hepatic injury, Stevens-Johnson Syndrome);
- (B) One or more occurrences of an event that is not commonly associated with drug exposure, but is otherwise uncommon in the population exposed to the drug (e.g., tendon rupture);

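### AE collection has no single end date: three sections require 100 days after dosing, Section 13.4.4 counts 7 or 30 days from an undefined date, and no visit listed after the End of Treatment and safety visits reviews AEs

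*Combined protocol and SAP*

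**What the plan says.** **How long to collect.** Section 13.3 says that non-serious AEs "should be collected continuously during the treatment period and for a minimum of (100 days) days following the last dose of study treatment". Section 13.6 says that SAEs "through 100 days of discontinuation of dosing must be reported to BMS Worldwide Safety", and Section 13.7 repeats the 100 days. Section 13.4.4 gives another rule: events are recorded "until 7 (for non-serious AEs) or 30 days (for SAEs) after the last day of study participation". No section defines that day.

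**When to ask.** The text of Section 10 has "End of Treatment Visit, 28 days after the last dose of Nivolumab and Relatlimab combination treatment", with a window of 14 days either way. The calendar in Section 10.8 heads the same visit "EOT (at time of discontinuation", with a window of 3 days. Next comes "Safety Follow-Up, 30 days (+ or – 7 days) post discontinuation", which includes AE review, and then "Survival Follow-Up, Every 12 weeks (+ or – 7 days) for 2 years". Section 10.7 lists only post-study anticancer therapy and survival status for these contacts. The calendar row for AE review is blank in the survival column. Section 10.7 does not say from which date its 12 weeks run.

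**General rule.** Section 13.4.4 also says: "At each study visit, the investigator will inquire about the occurrence of AE/SAEs since the last visit".

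**The concern.** The safety profile (AEs and SAEs) is a secondary endpoint in Section 2, and Section 1.8.5 names immune-related AEs as the important identified risk. An event that starts after the last listed review but before day 100 must be collected under Section 13.3. Staff who work from the visit lists are not prompted to ask about it. Two coordinators who each follow the text could also apply different end dates under Section 13.4.4. Section 16.3 promises AE tabulations but sets no collection window, so it does not settle the matter. The AE tables might then not cover the same post-treatment period for every patient.

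**Working it through.** The plan gives no figure of its own on this point, so the check is day arithmetic. Days are counted from the last dose. I take the end of dosing in Sections 13.6 and 13.7 to be the last dose.

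**Inputs**

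- Required end of collection: day 100 (13.3, 13.6, 13.7).
- End of Treatment (EOT) visit under 10.5: 28 ± 14, so day 14 to 42.
- Safety visit: 30 ± 7 days after discontinuation (10.6). Whether discontinuation is the last dose or the decision to stop is not stated.
- Survival contacts: every 84 ± 7 days (10.7).
- Assumed decision dates: day 28 (next dose due on a 4-week cycle) to day 42 (the 6-week hold limit in Section 7).

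**1. Days with no listed AE review** (100 minus the day of the last listed review)

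- Discontinuation = last dose. The safety visit falls on day 23 to 37. The later of the safety and EOT visits falls on day 23 to 42. Gap: 100 − 42 = 58 to 100 − 23 = 77 days.
- Discontinuation = decision at day 28 to 42. The safety visit falls on day 28 + 23 = 51 to 42 + 37 = 79. Gap: 100 − 79 = 21 to 100 − 51 = 49 days.

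The second range is an example and not a bound. Section 7 requires permanent discontinuation for most drug-related Grade 4 toxicity, which can occur before day 28.

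**2. The same gap if the each-visit inquiry covers survival contacts**

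- 12 weeks run from the last dose: first contact on day 77 to 91. Gap: 100 − 91 = 9 to 100 − 77 = 23 days. These days are reached only at the second contact, about 12 weeks later.
- 12 weeks run from the safety visit (itself counted from the last dose): first contact on day 23 + 77 = 100 to 37 + 91 = 128. No gap.

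**3. Where Section 13.4.4 ends recording**

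| Reading of the last day of participation | Non-serious (+7) | SAE (+30) | Days short of 100: non-serious / SAE |
|---|---|---|---|
| End of 2-year follow-up, about day 730 | day 737 | day 760 | none / none |
| 5.12 completion, last listed laboratory tests on day 23 to 42 (discontinuation = last dose) | day 30 to 49 | day 53 to 72 | 51 to 70 / 28 to 47 |
| 5.12 completion, last listed laboratory tests on day 51 to 79 (decision at day 28 to 42) | day 58 to 86 | day 81 to 109 | 14 to 42 / 0 to 19 |

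The two rows based on 5.12 are illustrations. They place the last study laboratory test at the EOT or safety visit. Correlative blood is also due at progression or response (10.2, Section 11), and in a consenting patient that can come later.

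**The case against.** **Section 13.4.4 need not conflict with 100 days.** A reader might infer that it cuts collection short. The documents do not establish that. The participant-duration entries in the Protocol Summary and in Section 3.1 (item 5) include the 2-year follow-up and give a total of about 3 years. Section 6.1 says that stopping the drugs is not leaving the study. Section 5.12 defines completion of the study and not participation. On the longer reading there is no shortfall. What stands is that the term is undefined and that Section 5.12 leaves a shorter reading open.

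**The duty to ask already exists.** A reader might take the 58 to 77 days as unobserved time. That also goes too far. Section 10.7 calls its contact a visit, so the each-visit rule can be read to cover it. Section 13.7 also asks for later SAEs believed related to study drug or a protocol procedure. These duties reduce the risk considerably. They are not carried into Section 10.7 or the calendar, and the Section 13.7 provision does not extend to non-serious events.

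**The last-dose reading is awkward.** It would put the calendar's EOT visit on the final dosing day, within 3 days. A decision made when the next dose is due fits the calendar better and gives the smaller gap. This is fair, and both ranges are therefore given.

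**The EOT dates disagree, so both visits might be tied to the last dose.** The disagreement between 10.5 and the calendar is real, but this remedy would do harm. EOT would fall on day 14 to 42 and the safety visit on day 23 to 37, almost together and with nearly the same assessments. For decisions at day 28 to 42, the last physical and laboratory review would move from day 51 to 79 back to day 42 at the latest.

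**No effect on a safety result is shown.** That is correct. The analysis is a descriptive single-arm tabulation, and the size can be given only in days.

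**Conclusion.** The point holds as an unresolved inconsistency in when AE collection ends, together with a 100-day duty that is missing from the visit schedule. The listed schedule leaves 58 to 77 of the 100 days without AE review if discontinuation means the last dose. It leaves fewer, for example 21 to 49, if discontinuation means a decision at day 28 to 42. Applying the each-visit inquiry to survival contacts reduces this to 9 to 23 days after the first contact, or to none, depending on where the 12 weeks start. A shortfall in Section 13.4.4 itself arises only on the 5.12 reading.

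The consequence is possible incompleteness and uneven follow-up in late AE counts. The documents give no basis for estimating how many events would be missed. Nothing here bears on the objective response rate or the Simon error rates. The guideline in Section 15.4 counts toxicity during study treatment, so it is not affected either.

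**What to change.** 1. **Section 13.4.4:** replace the 7 and 30 days with *until 100 days after the last dose* for both non-serious AEs and SAEs. Keep the Section 13.7 rule for later related SAEs.
2. **Sections 10.7 and 10.8:** set the first survival contact at day 100 (+14) after the last dose, by visit or telephone, and mark AE review for it in the calendar. Alternatively, add AE/SAE inquiry to each survival contact until one falls on or after day 100.
3. **Leave unchanged:** the safety visit at 30 (± 7) days post discontinuation, and Section 15.4. Do not re-anchor the EOT or safety visit to the last dose.

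**Cost.** The change is wording plus at most one extra telephone contact per patient (up to 27) if the 12-week contact is also kept. If the first survival contact is moved instead, and the 12 weeks were meant to run from the last dose, it comes 100 − 91 = 9 to 114 − 77 = 37 days later than now. Dates of death are still recorded. If the 12 weeks were meant to run from the safety visit (day 100 to 128), day 100 to 114 is no later overall. The sample size does not change.
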